Neurocognitive symptoms	Clinical: During Part 2A (multiple ascending doses) of Study 214760, neurocognitive symptoms such as feeling of 'hangover', brain fog, nightmare and drowsiness were reported. A clear causal relationship between these events and GSK3965193 has not been established; however, these types of events will be closely monitored, and appropriate risk mitigation has been included in the protocol.	General Measures: Neurocognitive events are categorized as Adverse Events of Special interest (AESIs) which must be reported to the Medical Monitor within 24 hours regardless of study drug relationship.  Monitoring & Stopping Criteria:  Assess baseline cognition using the Modified Mini-Mental Status Exam (MMSE). Repeat testing should be performed at the discretion of the Investigator should any concerns be raised alongside an assessment as to whether study treatment should be discontinued.  Individual participant and study level stopping criteria are defined in Section 7.1.4 as are sponsor actions taken in response to study stopping.  ,

Clinical Study Protocol template V15 dated 21-Dec-2020

Signals or Potential Risk of Clinical Significance	Summary of Data/Rationale for Risk	Mitigation Strategy
Effect on human embryo/fetus	Nonclinical: Preliminary animal embryofetal studies suggest minimal risk for the developing human embryo or fetus at the proposed clinical dose range. Women of childbearing potential (WOCBP) can receive GSK3965193 in a clinical study if they use proper contraception as required by the study protocol to avoid pregnancy while taking part in the study.	
Pregnant women will not be eligible to participate.
 
Participating WOCBP (applicable to Parts 3 and 4 only) will agree to comply with the study contraception requirements. Participants will be withdrawn from the study if the participants become pregnant during the study.
 
Pregnancy tests will be done at screening, before dosing, and after completion of dosing.
 
Refer to Section 10.4.3 for detailed information regarding collection of pregnancy information

Bepirovirsen		

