### Population:

1. Part 1 and Part 2: Healthy participants
2. Part 3 and Part 4: PLWCHB treated on stable NA therapy

**Table 1**      **Estimand framework for Safety for Part 1 and Part 2 in Healthy participants and Part 3 (GSK3965193 monotherapy) and Part 4 (combined with Bepirovirsen) in PLWCHB**

Estimand Category	Estimand		
	Variable/Endpoint	Intercurrent Event Strategy	Population Level Summary Measure
First Main Estimand  Primary Objective 1: To assess the safety and tolerability of oral administration of GSK3965193	Incidence of AEs, SAEs, and AEs leading to withdrawal  Incidence of clinically significant laboratory parameters (haematology, clinical chemistry, urinalysis), vital signs, and cardiac parameters (electrocardiogram [ECG]), and sensory nerve conduction (Parts 2, 3, 4)	Part 1: Single dose. No intercurrent event identified  Part 2, 3 and 4: Intercurrent event of discontinuation of, interruption in, and non-adherence to GSK3965193 will be handled by treatment policy strategy, i.e., regardless of the intercurrent event occurring	Categorical variables: proportions  Continuous variables: mean, standard deviation, median, minimum, and maximum
Second Main Estimand  Secondary Objective 3 Part 3: To assess the safety and tolerability of bepirovirsen monotherapy in PLWCHB who have completed GSK3965193 monotherapy	Incidence of AEs, SAEs, and AEs leading to withdrawal  Incidence of clinically significant laboratory parameters (haematology, clinical chemistry, urinalysis), vital signs, and cardiac parameters (electrocardiogram [ECG]), and sensory nerve conduction (Parts 2, 3, 4)	Intercurrent event of discontinuation of, interruption in, and non-adherence to GSK3965193 will be handled by treatment policy strategy, i.e., regardless of the intercurrent event occurring	Categorical variables: proportions  Continuous variables: mean, standard deviation, median, minimum, and maximum

**Table 2**      **Estimand framework for PD for Part 3 (GSK3965193 monotherapy) and Efficacy and PD for Part 4 (concurrently GSK3965193 with Bepirovirsen) in PLWCHB**

Estimand Category	Estimand (Part 3 and Part 4)		
	Variable/Endpoint	Intercurrent Event Strategy	Population Level Summary Measure

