Primary Objective 2: To evaluate PD effect of GSK3965193 monotherapy in PLWCHB (Part 3)  First Main Estimand	
 
Maximum reduction of serum HBsAg levels from baseline CCI [REDACTED]
 
	
 
Hypothetical strategy, discontinuation of, interruption in, and non-adherence to GSK3965193 related to or not related to any wide disruptive events will be handled assuming they had not happened (hypothetical strategy).
 
	
 
Mean averaged over all PLWCHB in each treatment group
 

Primary Objective 3: To evaluate efficacy of GSK3965193 in combination with bepirovirsen (Part 4)  Second Main Estimand	
 
Achieving complete response (undetectable serum HBV DNA and HBsAg for 6 months after the planned end of treatment of bepirovirsen)
 
	
 
Intercurrent event of discontinuation of, interruption in, and non-adherence to GSK3965193 not related to any wide disruptive events and for change in the background NA therapy will be ignored (treatment policy strategy)
 
Wide disruptive events (such as COVID-19 pandemic) leading to discontinuation of, interruption in, and non-adherence to bepirovirsen and GSK3965193 will be handled assuming they had not
 
	
 
Proportion of PLWCHB
 

Estimand Category	Estimand (Part 3 and Part 4)		
	Variable/Endpoint	Intercurrent Event Strategy	Population Level Summary Measure
		happened (hypothetical strategy).	
Secondary Objective 1: To evaluate pharmacodynamic (PD) effect of GSK3965193 monotherapy in PLWCHB (Part 3) Third Main Estimand	
 
• <math>\geq 0.5 \times \log</math> IU/mL reduction of serum HBsAg levels from baseline any time during the study (on-treatment and post-treatment)
 
	
 
• Same as Primary Objective 2 for Part 3
 
	
 
• Proportion of PLWCHB
 

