## 7. DISCONTINUATION OF STUDY INTERVENTION AND PARTICIPANT DISCONTINUATION/WITHDRAWAL

### 7.1. Discontinuation of Study Treatment

In rare instances, it may be necessary for a participant to permanently discontinue study treatment. A participant may discontinue study treatment at any time at his/her own request. Additionally, study treatment may be withdrawn at any time at the discretion of the Investigator for safety, behavioural or administrative reasons.

If study treatment is permanently discontinued, the participant will remain in the study to be evaluated for safety and efficacy assessments. If a participant discontinues study treatment, an early discontinuation (ED) visit should be performed. See the SoA for data to be collected at the time of discontinuation of study treatment.

Following the ED visit the participant will enter the follow-up/post-treatment period following the visit schedule and required assessments that need to be completed, per the SoA.

In Part 3 of the study participants who discontinue study treatment during the GSK3965193 (or placebo) monotherapy phase should complete an ED visit and enter the two-week CCI follow-up/washout period. If the participant CCI and consented to optional bepirovirsen, progression into the optional bepirovirsen treatment period must not occur unless this has been discussed and agreed with the Medical Monitor prior to the day 43 visit.

If the patient withdraws consent to participate in the study completely the procedure described in Section 7.2 should be followed.

Stopping criteria, including their evaluation and confirmation, are detailed in Section 7.1.1 to Section 7.1.7. Participants meeting these criteria should be monitored until laboratory abnormalities resolve, stabilize, or return to within baseline values as indicated. This may be done at follow-up visits specified in the SoA or require additional visits to be scheduled.

Study treatment may be discontinued, and the participant potentially withdrawn from the study, if:

- A participant experiences a serious or severe clinically significant AE that in the clinical judgement of the Investigator, is possibly, probably or definitely related to investigational product.
- The participant initiates treatment with any prohibited medications.
- Individual or study level stopping criteria are met
- Deviation(s) from the protocol
- Withdrawal of consent by participant (or proxy)
- Discretion of the Investigator

- Participant is lost to follow-up

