## **7.2. Participant Discontinuation/Withdrawal from the Study**

- A participant may withdraw from the study at any time at his/her own request or may be withdrawn at any time at the discretion of the investigator for safety, behavioural, or compliance reasons. This is expected to be uncommon.
- At the time of discontinuing from the study, if possible, an early discontinuation visit should be conducted, as shown in the SoA. See SoA for data to be collected at the time of study discontinuation and follow-up and for any further evaluations that need to be completed.
- The participant will be permanently discontinued both from the study intervention and from the study at that time.
- If the participant withdraws consent for disclosure of future information, the sponsor may retain and continue to use any data collected before such a withdrawal of consent.
- If a participant withdraws from the study, he/she may request destruction of any samples taken and not tested, and the investigator must document this in the site study records.

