### 8.3.5. Pregnancy

- Details of all pregnancies in female participants and female partners of male participants will be collected after the start of study intervention and until completion of the final follow up visit.
- If a pregnancy is reported, the investigator will record pregnancy information on the appropriate form and submit it to GSK within 24 hours of learning of the female participant pregnancy. While pregnancy itself is not considered to be an AE or SAE, any pregnancy complication or elective termination of a pregnancy for medical reasons will be reported as an AE or SAE.
- Abnormal pregnancy outcomes (e.g., spontaneous abortion, fetal death, stillbirth, congenital anomalies, ectopic pregnancy) are considered SAEs and will be reported as such.

- Any termination of pregnancy will be reported, regardless of fetal status (presence or absence of anomalies) or indication for procedure.
- The participant/pregnant female partner will be followed to determine the outcome of the pregnancy. The investigator will collect follow-up information on the participant/pregnant female partner and the neonate and the information will be forwarded to the sponsor.
- Any post-study pregnancy-related SAE considered reasonably related to the study intervention by the investigator will be reported to the sponsor as described in Section 10.3 (Appendix 3). While the investigator is not obligated to actively seek this information in former study participants, he or she may learn of an SAE through spontaneous reporting.
- Any female participant who becomes pregnant while participating in the study will discontinue study intervention or be withdrawn from the study.

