### 10.4.3. Collection of Pregnancy Information

Information regarding all pregnancies in female participants and female partners of male participants will be collected as follows:

- Investigators will collect pregnancy information on any female participant, who becomes pregnant while participating in this study (pregnant participant).
- Investigators will collect pregnancy information on any female partner of a male participant, who becomes pregnant whilst the male participant is participating in this study (pregnant partner).
- The initial information will be recorded on the appropriate form and submitted to GSK within 24 hours of learning of a participant's or participant's partner's pregnancy.
- The pregnant participant/partner will be followed to determine the outcome of the pregnancy. The investigator will collect follow up information on participant/partner and neonate, which will be forwarded to GSK. Generally, follow-up will not be required for longer than 6 to 8 weeks beyond the estimated delivery date.
- Any termination of pregnancy will be reported, regardless of fetal status (presence or absence of anomalies) or indication for procedure.
- While pregnancy itself is not considered to be an AE or SAE, any pregnancy complication or elective termination of a pregnancy for medical reasons will be reported as an AE or SAE.
- A spontaneous abortion (occurring at 22 weeks gestational age) is always considered to be an SAE and will be reported as such.
- Any SAE occurring as a result of a post-study pregnancy which is considered reasonably related to the study intervention by the investigator, will be reported to GSK as described in Section 10.3 (Appendix 3). While the investigator is not obligated to actively seek this information in former study participants, he or she may learn of an SAE through spontaneous reporting.

Any female participant who becomes pregnant while participating:

- will discontinue study intervention or be withdrawn from the study

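### Section 2.3.1 requires study withdrawal on pregnancy while 8.3.5 and 10.4.3 also allow stopping drug only, so follow-up that 7.1 would keep may be lost

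*Protocol*

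**What the plan says.** Women of childbearing potential can enter Parts 3 and 4 only. Three places in the protocol say what happens if one becomes pregnant.

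- Section 2.3.1, embryo/fetus row of the risk table: "Participants will be withdrawn from the study if the participants become pregnant during the study". No alternative is offered. The same row sends the reader to 10.4.3 for collecting pregnancy information.
- Section 8.3.5: "Any female participant who becomes pregnant while participating in the study will discontinue study intervention or be withdrawn from the study".
- Section 10.4.3 repeats the either/or rule: she "will discontinue study intervention or be withdrawn from the study".

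The two actions lead to different follow-up. For stopping treatment, Section 7.1 says: "If study treatment is permanently discontinued, the participant will remain in the study to be evaluated for safety and efficacy assessments". After an early discontinuation visit she moves to the post-treatment schedule. For leaving the study, Section 7.2 says: "The participant will be permanently discontinued both from the study intervention and from the study at that time". That section asks for an early discontinuation visit if possible and refers to the Schedule of Activities for any further evaluations. The schedules are redacted.

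**The concern.** One event has a mandatory rule in one section and a choice in two others, and nothing visible ranks them. A site that follows 2.3.1 removes a participant whom 7.1 would have kept. Stopping drug already ends exposure, and no visible text gives a further reason for removing her from follow-up.

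Two kinds of data are at stake.

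- **Safety, Parts 3 and 4.** Section 8.3.1 collects adverse events to the final follow-up visit, and does not oblige investigators to seek new events once participation has ended.
- **Part 4 primary efficacy.** Section 8.1 needs HBsAg and HBV DNA below LLOQ at the end of bepirovirsen and for 24 weeks afterwards. A withdrawn participant stays in the ITT population (Section 9.3), possibly with no determinable outcome.

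**Working it through.** No figure in the plan is to be reproduced. The check is a comparison of text, followed by what can be said about size.

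**Which action satisfies which section**

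| Action on pregnancy | 2.3.1 | 8.3.5 | 10.4.3 | Scheduled follow-up |
|---|---|---|---|---|
| Withdraw from study | met | met | met | participation ends (7.2) |
| Stop drug, stay in study | not met | met | met | continues (7.1) |

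Only the second action clearly keeps scheduled safety and efficacy visits, and it is the one that 2.3.1 rules out.

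**What survives withdrawal.** Four things remain: the early discontinuation visit if possible; whatever the redacted schedule asks for; follow-up of existing adverse events until resolved or stabilized (8.3.3); and pregnancy-outcome follow-up (8.3.5, 10.4.3).

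**Whose Part 4 outcome is open.** While on bepirovirsen, everyone's is. In follow-up, it is open only for a participant still below LLOQ on both markers. One who is above LLOQ at planned end of treatment, or has a confirmed rebound, is already a non-responder and loses no primary outcome. If earlier bepirovirsen results hold (9 to 10% sustained response, Section 2.2), at least that share would still be open in follow-up.

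**How far the estimands reach.** For safety, Table 1 reads: "Part 2, 3 and 4: Intercurrent event of discontinuation of, interruption in, and non-adherence to GSK3965193 will be handled by treatment policy strategy". Table 2 likewise uses treatment policy for stopping GSK3965193 in the Part 4 primary estimand, outside wide disruptive events. Treatment policy needs data after stopping, so withdrawal works against it, but only when pregnancy stops GSK3965193. Section 4.2.4 indicates that bepirovirsen continues alone after 28 days.

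**Part 3 primary PD.** SAP 1.1.1 uses data only up to discontinuation of dosing, so a withdrawal for a pregnancy that stops GSK3965193 removes nothing from that analysis.

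**Size (Part 4).** The bepirovirsen duration is redacted. Assume 12 to 24 weeks (24 is the Part 3 optional arm, SAP 4.5.1; 12 is an assumption), with the last dose at planned end.

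- Response window: 24 × 7 = 168 days.
- First dose to end of window: 84 + 168 = 252 days, or 168 + 168 = 336 days.
- Part reached by the treatment-policy argument, taking GSK3965193 as 28 days: 28/252 = 11%, or 28/336 = 8%.
- Days after the 90-day contraception requirement (5.1.1): 168 − 90 = 78. In those days no study drug is left to stop, yet 2.3.1 still requires removal. A pregnancy conceived late in this span would be found only after week 24, so fewer than 78 days count.
- Days under required contraception: 84 + 90 = 174, or 168 + 90 = 258. At the ceiling of 1% failure per year (5.1.1): 174/365 × 1% = 0.48%, or 258/365 × 1% = 0.71%, per woman of childbearing potential with consistent and correct use. After that period the rate is unknown.

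The count of such women and the arm sizes are not visible, so an expected number cannot be given.

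**The case against.** The strongest reply is that 2.3.1 is stricter, not incompatible. A site that withdraws the participant complies everywhere, and correcting 2.3.1 alone would not stop that, because 8.3.5 and 10.4.3 permit withdrawal too. This stands, and it is why the fix must touch all three sections. The sentence also sits in a mitigation summary under the GSK3965193 heading, and Section 8.2.8 sends an investigator with a reported pregnancy to 8.3.5. That makes the strict rule less likely to be applied, but does not remove it.

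A reader might infer that withdrawal ends all data collection. The documents do not show this: 7.2 defers further evaluations to a schedule that cannot be seen, and adverse-event and pregnancy-outcome follow-up continue. Withdrawn participants may also be replaced (4.2.3 for Part 3 monotherapy, 4.2.4 for Part 4), which protects numbers but not her own outcome.

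A reader might also infer that every pregnancy withdrawal defeats the treatment-policy estimands. It does not. The text cited covers GSK3965193 only, so it does not reach a pregnancy after that dosing has ended, including one in the 78 days above.

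Finally, keeping pregnant participants in an early-phase study by default is partly a sponsor and ethics judgement. That is fair. It is met by leaving both her consent and the investigator's power under 7.2 intact.

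**Conclusion.** The inconsistency is real and in current, unredacted text. Section 2.3.1 mandates withdrawal, 8.3.5 and 10.4.3 permit an alternative, and only the alternative clearly keeps scheduled follow-up. The loss is possible rather than certain. It consists of scheduled safety follow-up in Parts 3 and 4 and, in Part 4, a 24-week response that is still open. The 90-day contraception minimum is not itself a defect.

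Severity is minor, and the change is a cheap improvement. Confidence is high on the wording and its direction, and low on any count of participants. The day counts and the 0.48% to 0.71% ceiling rest on the assumed bepirovirsen duration. How a missing Part 4 outcome would be handled is not visible: the protocol text is redacted and the SAPs supplied cover Parts 1 to 3.

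**What to change.** In 2.3.1, replace the sentence with a cross-reference to 8.3.5. In 8.3.5 and 10.4.3, state that a participant who becomes pregnant discontinues any remaining study intervention and stays in the study for scheduled safety and HBsAg/HBV DNA visits as in 7.1. Make two exceptions: she withdraws consent, or the investigator withdraws her for safety under 7.2, which already says a participant "may be withdrawn at any time at the discretion of the investigator for safety, behavioural, or compliance reasons".

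Stopping drug on pregnancy is unchanged, and no analysis changes. The cost is a wording amendment in three sections, plus continued visits and blood draws for a rare participant, which she may decline.

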### 2.3.2. Benefit Assessment

The first two parts of this study were conducted in healthy participants; no direct medical benefit was derived by their participation.

Part 3 will be conducted in PLWCHB on stable NA therapy with GSK3965193/Placebo CCI followed by CCI of bepirovirsen treatment.

Participants may demonstrate a lowered HBsAg, but no durable medical benefit will be expected CCI GSK3965193 treatment period; however, participants will be making a valuable contribution to scientific knowledge of the treatment of CHB.

Participants on stable NA therapy with HBsAg levels CCI at screen who opt to receive open label bepirovirsen after GSK3965193 treatment may experience a moderate rate of sustained HBsAg and HBV DNA loss 12% [Yuen, 2022].

Part 4 will study the safety and efficacy of GSK3965193 in combination with bepirovirsen CCI. There is a need in patients with CHB for a finite treatment that allows them to achieve immune control of their infection (complete response, defined as HBsAg and HBV DNA below LLOQ for 6 consecutive months after the planned end of treatment), removing the need for lifelong therapy and to improve long term disease outcomes, particularly development of hepatocellular carcinoma. CCI

CCI  
CCI  
CCI  
CCI  
CCI

#### 2.3.2.1. Overall Benefit: Risk Conclusion

The potential risks associated with GSK3965193 alone and in combination with bepirovirsen can be appropriately mitigated by the careful selection of study participants and the proposed safety monitoring procedures. As such, the risk to potential participants is considered low.

Considering the measures taken to minimize risk to participants in this study, the potential risks identified in association with GSK3965193 alone and in combination with bepirovirsen are justified by the anticipated benefits that may be afforded by the future development of a new therapy for patients with CHB.

### 3. OBJECTIVES AND ENDPOINTS AND ESTIMANDS

[figure not shown]
Objectives	Endpoints
Part 1 and Part 2 (healthy participants)	
Primary	

 
To assess the safety and tolerability of oral administration of GSK3965193
 
	
 
Incidence of adverse events (AEs), serious adverse events (SAEs), withdrawals due to AEs
 
Incidence of clinically significant laboratory parameters (haematology, clinical chemistry, urinalysis), vital signs, cardiac parameters (electrocardiogram [ECG]), and sensory nerve conduction (Part 2)
 

 
To evaluate the PK characteristics of single and repeat doses of GSK3965193
 
	
 
Area under the plasma-concentration time curve (AUC): <math>AUC_{(0-\infty)}</math> for single dose and <math>AUC_{(0-\tau)}</math> for repeat dose, maximum observed plasma drug concentration (<math>C_{max}</math>), time to maximum observed plasma drug concentration (<math>T_{max}</math>), and apparent terminal half-life (<math>T_{1/2}</math>) will be calculated as data permits per part
 

Secondary	

 
To investigate the effect of food on the PK characteristics of CCI [REDACTED] of GSK3965193
 
	
 
Area under the plasma-concentration time curve (AUC): <math>AUC_{(0-\infty)}</math>, and maximum observed plasma drug concentration (<math>C_{max}</math>) as data permits
 

Exploratory	

CCI

Objectives	Endpoints

 
To investigate metabolites in plasma, urine and bile for GSK3965193
 
	
 
Metabolite identification and concentration measurement in plasma, urine and bile (Part 2 only)
 

Part 3 and Part 4 (participants living with chronic hepatitis B infection [PLWCHB])	
Primary	

 
To assess the safety and tolerability of oral administration of GSK3965193 monotherapy (Part 3) and in combination with bepirovirsen (Part 4)
 
	
 
Incidence of AEs, SAEs, withdrawals due to AEs
 
Incidence of clinically significant laboratory parameters (haematology, clinical chemistry, urinalysis), vital signs, cardiac parameters (electrocardiogram), and sensory nerve conduction
 


 
To evaluate pharmacodynamic (PD) effect of GSK3965193 monotherapy in PLWCHB (Part 3)
 
	
 
Maximum reduction of serum HBsAg levels from baseline CCI [REDACTED]
 

 
To evaluate efficacy of GSK3965193 in combination with bepirovirsen in PLWCHB (Part 4)
 
	
 
Achieving complete response (undetectable serum HBV DNA and HBsAg for 6 consecutive months after the planned end of treatment of bepirovirsen)
 

Secondary	

 
To evaluate the PK characteristics of repeat doses of GSK3965193 in PLWCHB (Part 3)
 
	
 
AUC(0-tau), Cmax, Tmax, and apparent terminal half-life (T1/2) will be calculated as data permits
 

 
To evaluate pharmacodynamic (PD) effect of GSK3965193 monotherapy in PLWCHB (Part 3)
 
	
 
≥0.5x log IU/mL reduction of serum HBsAg levels from baseline anytime during the study (on-treatment and post-treatment)
 

 
To assess the safety and tolerability of bepirovirsen monotherapy in PLWCHB who have completed GSK3965193/placebo monotherapy (Part 3)
 
	
 
Incidence of AEs, SAEs, withdrawals due to AEs
 
Incidence of clinically significant laboratory parameters (haematology, clinical chemistry, urinalysis) and vital signs
 

Objectives	Endpoints

To evaluate PD effect of GSK3965193 in combination with bepirovirsen in PLWCHB (Part 4)

	

HBsAg loss (defined by two consecutive measurements of HBsAg below the limit of quantification) anytime during the study (on-treatment and post-treatment)

Exploratory	

CCI

Objectives	Endpoints
CCI	

